13.5.3. Reporting Standards for Pharmacokinetic

Concentration Data	
Descriptive Summary Statistics	Refer to IDSL Statistical Principle 6.06.1 Assign zero to NQ values (Refer to GUI_51487 for further details)
Pharmacokinetic Parameters	
Descriptive Summary Statistics (Log Transformed)	N, n, geometric mean, 90% CI of geometric mean, standard deviation (SD) of logged data and between geometric coefficient of variation (CVb (%)) will be reported.

CONFIDENTIAL

209275

	
CVb (%) = $\sqrt{(\exp(\text{SD}^2) - 1) * 100}$ [NOTE: SD = SD of loge transformed data]
 
Following steps can be used to calculate 90% CI for PK parameters: Standard Error = [(Geometric Stdev-1)/Sqrt(N)], Margin of Error = [Standard Error * 1.645], and CI = [Geometric Mean ± Margin of Error]

Parameters Not Being Log Transformed	tmax, t _{1/2}
Summary Tables	Cmax, tmax, AUC(0-τ), AUC(0-t), AUC (0-∞), AUC (Ro), Rcmx, Cτ, t1/2, Rss, Ae, fe, CLr, as data permit
Listings	Include PK Parameters Cmax, tmax, AUC(0-τ), AUC(0-t), AUC (0-∞), AUC (Ro), Rcmx, Cτ, t1/2, Rss, Ae, fe, CLr, as data Permit
Graphical Displays	
Refer to IDSL Statistical Principles 7.01 to 7.13 and Standards for the Transfer and Reporting of PK Data using HARP.	

Pharmacokinetic Concentration Data	
PC Windows Non-Linear (WNL) File	PC WNL file (CSV format) for the noncompartmental analysis by Clinical Pharmacology Modelling and Simulation function will be created according to [Insert document name]. Note: Concentration values will be imputed as per GUI_51487
Descriptive Summary Statistics, Graphical Displays and Listings	Refer to IDSL PK Display Standards. Refer to IDSL Statistical Principle 6.06.1. Note: Concentration values will be imputed as per GUI_51487 for descriptive summary statistics/analysis and summarized graphical displays only.
Pharmacokinetic Parameter Derivation	
PK Parameter to be Derived by Programmer	The following PK parameters will be derived by the Programmer: [Insert PK parameters, e.g. C24, C12, AUC/Dose]
Pharmacokinetic Parameter Data	
Is NQ impacted PK Parameters Rule Being Followed	No.
Descriptive Summary Statistics, Graphical Displays and Listings	Refer to IDSL PK Display Standards.

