2.2. Study Objective(s) and Endpoint(s)

[figure not shown]
Objectives	Endpoints
Primary Objectives	Primary Endpoints
To assess the safety and tolerability of GSK3439171A following single and repeat doses in healthy participants	Adverse events (AE), Serious Adverse Events (SAE), clinical laboratory values, vital signs, and electrocardiograms (ECG)
To characterize the PK of GSK3439171A, following single and repeat doses in healthy participants	Derived PK parameters for GSK3439171A including area under the plasma drug concentration versus time curve (AUC(0-t), AUC(0-inf), maximum observed plasma drug concentration (Cmax), time to maximum observed plasma drug concentration (tmax), and apparent terminal half-life (t1/2) as appropriate
Secondary Objectives	Secondary Endpoints
To assess the effect of food on the PK of GSK3439171A following an oral dose in healthy participants	Derived PK parameters for GSK3439171A including area under the plasma drug concentration versus time curve (AUC(0-t), AUC(0-inf), maximum observed plasma drug concentration (Cmax), time to maximum observed plasma drug concentration (tmax), and apparent terminal half-life (t1/2) as appropriate
To assess preliminary dose proportionality of GSK3439171A following single and repeat oral doses, as data permit	AUC(0-t), AUC(0-inf), and Cmax following single dose and AUC(0-τ) and Cmax following repeat dose for the assessment of dose proportionality
To examine the extent of accumulation and achievement of steady-state following repeat oral doses of GSK3439171A, as data permits	
 Determine observed accumulation based on AUC(Ro) and Cmax (RCmax) and determine the steady-state ratio (Rss) Trough plasma concentrations at the end of the dosing interval (Cτ) collected pre-dose for repeat doses 12, 13 and 14* to assess the achievement of steady-state of GSK3439171A
Exploratory Objectives	Exploratory Endpoints
To evaluate the PD properties of GSK3439171A	Levels of mediators on prostaglandin and/or inflammatory metabolic pathways such as, but not limited to, PGD2, and PGE2.
To assess the effect of GSK3439171A on QTc in healthy adult volunteers	Holter monitor data collection and storage for evaluation of the correlation between plasma levels of GSK3439171A and changes in the QTc interval in the future, if appropriate
To evaluate additional biomarkers of GSK3439171A target	Levels of change in novel biomarkers in blood, muscle, or urine, such as, but not limited to, urine

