10.1.2. Summary Measure

Refer to [Appendix 5](#): Data Display Standards & Handling Conventions (Section 13.5.3. Reporting Standards for Pharmacokinetic)

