13.12.7. Pharmacokinetic Tables

Pharmacokinetic: Tables					
No.	Population	IDSL / Example Shell	Title	Programming Notes	Deliverable [Priority]
PK concentration					
4.1.	PK	PK01	Summary of Plasma GSK3439171 Pharmacokinetic Concentration-Time Data (ng/mL) – Part A		SAC
4.2.	PK	PK01	Summary of Plasma GSK3439171 Pharmacokinetic Concentration-Time Data (ng/mL) – Part B		SAC
4.3.	PK	PK01	Summary of Plasma GSK3439171 Pharmacokinetic Concentration-Time Data (ng/mL) – Part C		SAC
PK Urine					
4.4.	PK	PK02	Summary of Pharmacokinetic Urine Excretion Rate-Time Data – Part B		SAC
PK derived parameters					
4.5.	PK	PK03	Summary Statistics of Derived Plasma GSK3439171 Pharmacokinetic Parameters – Part A		SAC
4.6.	PK	PK03	Summary Statistics of Derived Plasma GSK3439171 Pharmacokinetic Parameters – Part B		SAC
4.7.	PK	PK03	Summary Statistics of Derived Plasma GSK3439171 Pharmacokinetic Parameters – Part C		SAC
4.8.	PK	PK05	Summary Statistics of Log-Transformed Derived Plasma GSK3439171 Pharmacokinetic Parameters – Part A		SAC
4.9.	PK	PK05	Summary Statistics of Log-Transformed Derived Plasma GSK3439171 Pharmacokinetic Parameters – Part B		SAC

Pharmacokinetic: Tables					
No.	Population	IDSL / Example Shell	Title	Programming Notes	Deliverable [Priority]
4.10.	PK	PK05	Summary Statistics of Log-Transformed Derived Plasma GSK3439171 Pharmacokinetic Parameters – Part C		SAC
4.11.	PK	PK_T1	Statistical Analysis of Plasma GSK3439171 Pharmacokinetic Parameters: Analysis of Variance (ANOVA) – Part A	t1/2	SAC
4.12.	PK	PK_T1	Statistical Analysis of Plasma GSK3439171 Pharmacokinetic Parameters: Analysis of Variance (ANOVA) – Part B	t1/2 Include 'Visit' as first column	SAC
4.13.	PK	PK_T1	Statistical Analysis of Plasma GSK3439171 Pharmacokinetic Parameters: Analysis of Variance (ANOVA) – Part C	t1/2	SAC
4.14.	PK	PK_T2	Statistical Analysis of Log-Transformed Plasma GSK3439171 Pharmacokinetic Parameters: Analysis of Variance (ANOVA) – Part A	AUC(0-t), AUC(0-24), AUC(0-∞), Cmax, Cτ, AUC(Rp)	SAC
4.15.	PK	PK_T2	Statistical Analysis of Log-Transformed Plasma GSK3439171 Pharmacokinetic Parameters: Analysis of Variance (ANOVA) – Part B	AUC(0- τ), AUC(0-∞), Cmax, Cτ Include 'Visit' as first column	SAC
4.16.	PK	PK_T2	Statistical Analysis of Log-Transformed Plasma GSK3439171 Pharmacokinetic Parameters: Analysis of Variance (ANOVA) – Part C	AUC(0-t), AUC(0-∞), Cmax	SAC

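### The SAP's 90% CI recipe for geometric mean PK parameters adds a unitless margin to a mean that has units, so the limits depend on the reporting unit and coverage can fall to near 0%

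*SAP*

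**What the plan says.** SAP Section 13.5.3 specifies the descriptive statistics for log-transformed PK parameters as "N, n, geometric mean, 90% CI of geometric mean, standard deviation (SD) of logged data", together with the between-subject geometric CV. In the same cell the SD is defined: "SD = SD of loge transformed data". The recipe for the interval is introduced by "Following steps can be used to calculate 90% CI for PK parameters" and reads "Standard Error = [(Geometric Stdev-1)/Sqrt(N)], Margin of Error = [Standard Error * 1.645], and CI = [Geometric Mean ± Margin of Error". It does not multiply by the geometric mean and does not back-transform from the log scale.

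The row "Parameters Not Being Log Transformed" lists only tmax and t1/2. Of the primary PK endpoints in SAP Section 2.2, the recipe therefore reaches the AUCs and Cmax.

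Section 8.1.2 refers the primary PK summaries to Section 13.5.3. The tables concerned are 4.8 to 4.10, "Summary Statistics of Log-Transformed Derived Plasma GSK3439171 Pharmacokinetic Parameters", for Parts A, B and C. For PD summaries, Section 10.1.2 points to "Data Display Standards & Handling Conventions (Section 13.5.3. Reporting Standards for Pharmacokinetic". PD Tables 6.5 to 6.7 use the same shell (PK05) as Tables 4.8 to 4.10.

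**The concern.** A geometric mean AUC is in ng·h/mL or µg·h/mL. The geometric SD is exp(SD of logs), a ratio, so the margin built from it has no unit. The two cannot be added. If every value is multiplied by k to change the unit, the geometric mean becomes k times larger and the margin does not move, so the interval does not describe the same range of exposure. The margin is also the same for a Cmax of 10 and an AUC of 10,000 if their log-scale spread and n are the same.

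There are three smaller faults:

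- The interval is symmetric on the raw scale, although the data are treated as log-normal.
- It uses a normal quantile with 6 to 12 participants per group.
- It divides by √N, although the same row lists N and n separately.

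No hypothesis is tested in this study and the PK objectives rest on estimation. A reader of the report would take these intervals as the precision of the primary exposure estimates. In ng units they would look almost exact; in µg units at low doses they would include negative exposures. In Part A they would also stand beside the model-based intervals for the same parameters and doses (Table 4.14) and be incompatible with them.

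**Working it through.** **Inputs**

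- n = 6 per active dose in Part A (SAP 2.3); 9 active per cohort in Part B and 12 in Part C (protocol 9.2).
- CV 30%. This is an assumption: protocol Section 4.3 simulates clearance and volume with 30% between-subject variability, and I take that as the CV of AUC and Cmax. CVs of 15% and 50% were also run.
- True geometric means: the simulated means in protocol Table 2 (Section 6.6.1), taken as geometric means. This is also an assumption. They run from 0.10 to 9.85 µg·h/mL for AUC(0-inf) and from 0.01 to 1.20 µg/mL for Cmax.
- Units: planned Tables 4.1 to 4.3 give concentrations in ng/mL. The mock shells show AUC in µg·h/mL but are stated not to be study specific. Both scales were run.

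**The plan's own constant.** 1.645 is the 95th percentile of the standard normal, so the multiplier matches a two-sided 90% level. The 90% coverage does not reproduce.

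**Margin at CV 30%, n = 6**

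- SD of logs = √ln(1 + 0.30²) = 0.294; geometric SD = exp(0.294) = 1.341.
- Margin = 1.645 × (1.341 − 1)/√6 = 0.229, in whatever unit is chosen.

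**Same data, two units** (50 mg AUC, geometric mean 0.99 µg·h/mL)

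- SAP steps in µg·h/mL: 0.99 ± 0.229 = 0.761 to 1.219.
- SAP steps in ng·h/mL: 990 ± 0.229 = 989.77 to 990.23.
- Log-scale t interval: half-width 2.015 × 0.294/√6 = 0.2415 and exp(0.2415) = 1.273, so 0.99/1.273 to 0.99 × 1.273 = 0.778 to 1.260 µg·h/mL, which is 778 to 1,260 ng·h/mL.

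**Coverage of the nominal 90% interval** (100,000 log-normal samples per setting, CV 30%, n = 6)

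| Parameter, dose | µg units: mean, coverage | ng units: mean, coverage |
|---|---|---|
| AUC, 5 mg | 0.10, 100% (lower limit negative in 95% of samples) | 100, 1.5% |
| AUC, 50 mg | 0.99, 88% | 990, 0.14% |
| AUC, 100 mg | 1.97, 62% | not run |
| AUC, 300 mg | 5.91, 24% | not run |
| AUC, 500 mg | 9.85, 15% | 9,850, 0.02% |
| Cmax, 5 mg | 0.01, 100% (lower limit always negative) | 10, 14.6% |
| Cmax, 50 mg | not shown | 120, 1.2% |
| Cmax, 500 mg | 1.20, 82% | 1,200, 0.11% |

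A hand check on the 990 row: the standard error of the geometric mean is about 990 × 0.294/√6 = 119. An interval of ± 0.229 then covers about 2 × 0.229 × 0.399/119 = 0.15%, which agrees with the simulation.

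Across n = 6, 9 and 12 and CVs of 15% to 50% the pattern is the same; AUC in ng·h/mL is covered 0.01% to 1.7% of the time.

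**Variants at CV 30%, n = 6**

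- Multiplying the margin by the geometric mean: about 88%.
- Log-scale interval with 1.645: 84% (about 86% at n = 9 and 87% at n = 12).
- Log-scale interval with t(0.95, n−1) = 2.015 (1.860 at n = 9, 1.796 at n = 12): 90%, in either unit.

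**The case against.** The strongest reply is that the recipe is optional and its reach is narrow. The SAP says the steps can be used, not that they will be. The tables cite a standard sponsor shell that may compute the interval properly. The per-dose model estimates in Section 8.2.4 have their own log-scale 90% CIs, and dose proportionality, accumulation, steady state and food effect rest on those models. Dose escalation and the exposure limits use mean or individual AUC and Cmax, not CI limits. The slip may be no more than a dropped factor: geometric SD − 1 is close to the SD of the logs (0.341 against 0.294 here), so multiplying by the geometric mean would give a usable approximation.

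Much of this stands as a limit on the consequences. The model-based results and the conduct of the study are not touched. tmax and t1/2 are outside the recipe. For unitless ratios such as Ro, RCmax and Rss the unit argument does not apply. The PD reach comes only through a cross-reference and a shared shell, and the recipe itself names PK parameters. Coverage is also not always near zero; with small means in µg units the error runs the other way.

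None of it makes the formula right. Section 13.5.2 applies the sponsor's standards unless otherwise stated, and Section 13.5.3 states a formula and offers no other. The standard shell is not in the documents, so it cannot be relied on to override the text. The mixed models sit under the secondary PK analyses, so they do not replace the primary descriptive summaries. The proportional form is not a full repair either: at CV 50% it covers about 89%, 92% and 93% at n = 6, 9 and 12.

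**Conclusion.** The concern holds. That the limits depend on the unit follows from the formula alone and needs no assumption about the data. The size depends on the CV, the geometric mean and the reporting unit. At an assumed CV of 30% and n = 6, coverage of the nominal 90% interval runs from 0.02% for a large AUC in ng·h/mL to 100%, with negative lower limits, for low-dose exposures in µg units. Neither unit gives valid intervals across the dose range. The fault lies in the descriptive Tables 4.8 to 4.10 for AUC and Cmax, and in PD Tables 6.5 to 6.7 if they borrow the steps. It should be corrected before those tables are programmed, because they summarise primary PK endpoints and anyone following the text would code it as printed.

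**What to change.** In SAP Section 13.5.3, delete the three steps and write: 90% CI = exp( mean(ln x) ± t(0.95, n−1) × SD(ln x)/√n ), where n is the number of non-missing values for that parameter, dose and day. State that this applies to log-transformed parameters only. Name the tables it governs (4.8 to 4.10), and say in Section 10.1.2 whether it also governs PD Tables 6.5 to 6.7. Confirm that the PK05 shell produces the same interval.

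The cost is one line of SAP wording plus a check of the shell. The interval is standard software output, and neither the design nor the data collection changes.

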13.6. Appendix 6: Derived and Transformed Data

13.6.1. General

Multiple Measurements at One Analysis Time Point

 • Mean of the measurements will be calculated and used in any derivation of summary statistics but if listed, all data will be presented. • If there are two values within a time window the value closest to the target day for that window will be used. If values are the same distance from the target, then the mean will be taken. • Participants having both High and Low values for Normal Ranges at any post-baseline visit for safety parameters will be counted in both the High and Low categories of “Any visit post-baseline” row of related summary tables. This will also be applicable to relevant Potential Clinical Importance summary tables.
Study Day and Period Study Day

In PART A and C, Period Study day is calculated as the number of days from first Dose Date in the period for each subject as follows:
 
 • Ref Date = Missing → Period Study Day = Missing • Ref Date < First Dose Date in the period → Period Study Day = Ref Date – First Dose Date in the period • Ref Date ≥ First Dose Date in the period → Period Study Day = Ref Date – First Dose Date in the period + 1 
In Part A, B & C: Study day is calculated as the number of days from First Dose Date in each Cohort for each subject as:
 
 • Ref Date = Missing → Study Day = Missing • Ref Date < First Dose Date → Study Day = Ref Date – First Dose Date • Ref Date ≥ First Dose Date → Study Day = Ref Date – (First Dose Date) + 1
Change from baseline and Percentage change from baseline definition

Change from Baseline = Post-Dose Visit Value – Baseline (For Part A & C, corresponding period baseline should be considered as baseline)
 
Percentage Change from Baseline = ((Post-Dose Visit Value – Baseline)/Baseline)*100 (For Part A & C, corresponding period baseline should be considered as baseline)
 
 • Unless otherwise specified, the baseline definitions specified in Section 5.2 Baseline Definition will be used for derivations for endpoints / parameters and indicated on summaries and listings • Unless otherwise stated, if baseline data is missing no derivation will be performed and will be set to missing
Displays

- Compound ID should be used as GSK3439171 for the displays
- Listings: Since it is single site study, site id and investigator id will be included in 'Listing of Planned and Actual Treatment' and will be excluded from other Listings.
- Safety summaries and figures:
 - Part A and B, 'All treatment' total (Subjects on treatment except placebo) should be included and footnote to indicate this. Part C overall 'Total' should be included.
 - Part A and C, in Lab, Vitals and ECG displays, Day -2 and -1(if available) should be included for absolute value displays.
 - Part B in Lab, Vitals and ECG displays, Day -2 and -1(if available) should be included for absolute value displays along with screening and follow up data. And for change from baseline and percentage change from baseline displays follow up data should be included

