4. STUDY DESIGN

4.1. Overall Design

This is a three-part study (Parts A, B and C). Part A will be a double-blind (sponsor unblinded), single oral dose, dose-rising, placebo-controlled, randomized (with respect to placebo allocation), 3 period crossover study in approximately 3 cohorts of participants. Part B will be double-blind (sponsor unblinded), up to 14 day repeat oral dosing, placebo-controlled, randomized (with respect to placebo allocation), dose escalation study with at least three dose levels in 3 separate cohorts of participants who were not enrolled into Parts A or C of this study. Part C will be an unblinded, randomized, crossover study where a single dose will be administered fasted or fed conducted in a separate cohort of participants than those who were enrolled in Parts A or B.

The starting dose for Part A will be 5 mg (see Section 4.3.3).

Part A: Single Ascending Dose

Each participant will participate in 3 dosing periods and will receive 2 doses of GSK3439171A and 1 dose of placebo in a randomized fashion. There will be an approximately 7 day (or 5 half-lives, whichever is longer) washout period between dosing in each session.

Approximately 9 participants will be enrolled in each cohort. Participants will be admitted to the clinical unit on Day -2 and will remain in the unit until completion of assessments on Day 4 as outlined in the SoA. Participants will be discharged from clinical unit for the washout period between dosing sessions and will return approximately 14 days after dosing in their last dosing session for a follow-up visit. Participants will be randomized to treatment sequences such that in each period up to 6 participants will receive active dose and up to 3 participants will receive placebo. A minimum of three cohorts is anticipated. If a participant is withdrawn from the study, the participant may be replaced as necessary with another participant assigned to the same treatment sequence with respect to active and placebo doses to ensure that at least 4 participants receive each active dose and 1 participant receives a placebo, and that these participants complete safety and PK assessments through at least 72hr post-dose (or 5 half-lives, whichever is longer). Additional participants may be dosed at a given level if additional data are necessary to establish safety, tolerability or PK parameters prior to dose escalation.

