6.3. Measures to Minimize Bias: Randomization and Blinding

6.3.1. Randomization

Study using Pre-Coded Randomization provided to site	Before treatment begins at the beginning of each part of the study, participants will be assigned a unique number (randomization number) in ascending numerical order at the study site. The randomization number encodes the participant's assignment to the respective arms of the study, according to the randomization schedule generated prior to the study by the Clinical Statistics Department at GSK. Each participant will be dispensed blinded study intervention, labeled with his/her unique randomization number throughout the study.
---	--

In Part A, approximately 9 participants in each cohort will be randomized to one of 3 treatment sequences (AAP, APA & PAA, where A represents an active dose of GSK3439171 and P represents placebo). Within each period, allocation of active (A) to placebo (P) treatment will be 2:1. Within a cohort, an increasing dose of GSK3439171A will be administered in each period as illustrated in the table below. Planned doses are provided in Section 6.6. At each dose level, sentinel dosing will be employed, such that one subject is dosed with placebo and another with active dose of GSK3439171A and followed for 48 hr prior to the rest of the subjects receiving their randomized treatment.

Cohort	Sequence	Period 1	Period 2	Period 3
Cohort 1	AAP	D1	D2	Placebo
	APA	D1	Placebo	D3
	PAA	Placebo	D2	D3
Cohort 2	AAP	D4	D5	Placebo
	APA	D4	Placebo	D6
	PAA	Placebo	D5	D6
Cohort 3	AAP	D7	D8	Placebo
	APA	D7	Placebo	D9
	PAA	Placebo	D8	D9

In each cohort of Part B, approximately 12 participants will be randomized to receive either GSK3439171A or placebo in a parallel design using a 3:1 allocation ratio. Participants will receive a single dose followed by a 72 hr assessment period and then will receive daily repeat doses until the end of the study.

Dose Cohort	Regimen
B1	R1 mg GSK3439171A or placebo QD or BID
B2 ¹	R2 mg GSK3439171A or placebo QD or BID
B3 ¹	R3 mg GSK3439171A or placebo QD or BID

1. Dose levels for Cohorts will be determined based on real-time analysis of the safety, tolerability, PK, and preliminary PD data from Part A and therefore may be adjusted from predicted dose levels listed.

QD – Once daily

BID- Twice daily

Regimen	Period 1	Period 2
X	GSK3439171A ¹ administered in the fasted state	GSK3439171A ¹ administered after a high fat meal

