2.3. Study Design

Overview of Study Design and Key Features

Part A: Single Ascending Dose

Within a cohort, participants will be randomized to one of 3 treatment sequences such that each participant receives 2 active doses and 1 placebo dose resulting in each active dose being administered to 6 participants and placebo to 3 participants

[figure not shown]
- Starting dose (Dose 1) = 5 mg
- Subsequent dose escalations will be determined based on safety and PK data
- Maximum predicted dose = 500 mg (Genotoxic Risk Assessment Limit= 3000mg)
- Washout= 7 days or 5 half-lives, whichever is longer

= Dose escalation meeting

PBO= Placebo

*Note: dosing strategy is for illustrative purposes and does not represent the randomization strategy

[figure not shown]
Part B: Single and Repeat Dose 14-day dose-rising

Doses will be selected based on safety, tolerability and PK data from Part A

★ = Dose escalation meeting

Part C: Food Effect

☒ - 7-day or 5 half-lives (whichever is longer) washout period/ participant crossover to fasted/fed arm

Overview of Study Design and Key Features	
Design Features	
 • Part A is a randomized, double blind, placebo-controlled, crossover, single dose escalation study in healthy participants. Participants will be randomized to placebo or active study intervention groups after screening. • Part B is a randomized, double blind, placebo-controlled, parallel group, repeat dose escalation study in healthy participants. Participants will be randomized to placebo or active study intervention groups after screening. • Part C is a randomized, open label, crossover, food effect study in healthy participants. Participants will be randomized to fed or fasted groups after screening.

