5.1. Study Treatment & Sub-group Display Descriptors

Treatment Group Descriptions			
RandAll NG		Data Displays for Reporting	
Code	Description	Description	Order in TLF
Part A			
D1	GSK3439171A Dose 1	5 mg	2
D2	GSK3439171A Dose 2	10 mg	3
D3	GSK3439171A Dose 3	30 mg	4
D4	GSK3439171A Dose 4	60 mg	5
D5	GSK3439171A Dose 5	120 mg	6
D6	GSK3439171A Dose 6	180 mg	7
PA	Placebo Part A	Placebo	1
Part B			
DD1	GSK3439171A R1 mg QD or BID	5 mg	10
DD2	GSK3439171A R2 mg QD or BID	11 mg	11
DD3	GSK3439171A R3 mg QD or BID	40 mg	12
PB	Placebo Part B	Placebo	8
PB3	Placebo Part B Cohort 3	Placebo Cohort 3	9

Treatment Group Descriptions			
RandAll NG		Data Displays for Reporting	
Code	Description	Description	Order in TLF
Part C			
C1	GSK3439171A fasted	60 mg Fasted	13
C2	GSK3439171A fed	60 mg Fed	14

Note: If additional dose levels are explored in either Part A or B, then they will follow in a sequential order in the table

Treatment comparisons will be displayed as follows using the descriptors as specified:

1. Day 17 vs Day 1 (e.g.; Ro, RCmax and Rss)
2. Dose X.X mg vs Placebo
3. Repeat Dose X.X mg vs Placebo
4. Fasted vs Fed

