7. SAFETY ANALYSES

The safety analyses will be based on the safety population, unless otherwise specified.

Descriptive statistics will be used to assess safety and tolerability objectives. No formal statistical analyses of safety data are planned. Data will be summarized according to GSK Integrated Data Standards Library (IDSL) standards for Part A, Part B and Part C separately. In addition, individual participant data will be reviewed. Treatment comparisons with placebo will be based on review of descriptive statistics and individual participant data.

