3.20.	Safety	LB1	Summary of Chemistry Changes from Baseline - Part A	By dose and 'All Treatment' for all parameters mentioned in the protocol Includes Baseline values. Includes pre-specified parameters repeated in conventional units.	SR, SAC

Safety: Tables					
No.	Population	IDSL / Example Shell	Title	Programming Notes	Deliverable [Priority]
3.21.	Safety	LB1	Summary of Chemistry Changes from Baseline - Part B	By dose for all parameters mentioned in the protocol Includes Baseline values. Includes pre-specified parameters repeated in conventional units.	SR, SAC
3.22.	Safety	LB1	Summary of Chemistry Changes from Baseline - Part C	By treatment group (fed/fasted) and 'Total' for all parameters mentioned in the protocol Includes Baseline values. Includes pre-specified parameters repeated in conventional units.	SAC
3.23.	Safety	LB1	Summary of Chemistry Percent Changes from Baseline - Part A	By dose and 'All Treatment' for all parameters mentioned in the protocol Includes Baseline values. Baseline values are required Includes pre-specified parameters repeated in conventional units.	SAC
3.24.	Safety	LB1	Summary of Chemistry Percent Changes from Baseline - Part B	By dose for all parameters mentioned in the protocol Includes Baseline values. Baseline values are required Includes pre-specified parameters repeated in conventional units.	SAC

Safety: Tables					
No.	Population	IDSL / Example Shell	Title	Programming Notes	Deliverable [Priority]
3.25.	Safety	LB1	Summary of Chemistry Percent Changes from Baseline - Part C	By treatment group (fed/fasted) and 'Total' for all parameters mentioned in the protocol Includes Baseline values. Baseline values are required Includes pre-specified parameters repeated in conventional units.	SAC
Laboratory: Haematology					
3.26.	Safety	LB1	Summary of Haematology Values – Part A	By dose for all parameters mentioned in the protocol	SR, SAC
3.27.	Safety	LB1	Summary of Haematology Values – Part B	By dose for all parameters mentioned in the protocol	SR, SAC
3.28.	Safety	LB1	Summary of Haematology Values – Part C	By treatment group (fed/fasted) and 'Total' for all parameters mentioned in the protocol	SAC
3.29.	Safety	LB1	Summary of Haematology Changes from Baseline - Part A	By dose and 'All Treatment' (treatment vs placebo) for all parameters mentioned in the protocol	SR, SAC
3.30.	Safety	LB1	Summary of Haematology Changes from Baseline - Part B	By dose for all parameters mentioned in the protocol	SR, SAC

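### Part A's pooled 'All treatment' column gives each participant two active periods against one placebo period, so 'at least one event' rows show an excess on active even with no drug effect

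*SAP*

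**What the plan says.** Protocol 4.1 sets the Part A design: "Each participant will participate in 3 dosing periods and will receive 2 doses of GSK3439171A and 1 dose of placebo in a randomized fashion". SAP 2.3 repeats it. Protocol 6.3.1 uses the sequences AAP, APA and PAA and adds that "Within each period, allocation of active (A) to placebo (P) treatment will be 2:1".

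For Part A and Part B safety summaries and figures, SAP 13.6.1 instructs that an "All treatment' total (Subjects on treatment except placebo) should be included", with a footnote. The counting unit is subjects, and the footnote has only to explain that placebo is left out. Placebo is a separate column, first in the display order of SAP 5.1.

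SAP 7 plans no model for safety: "Treatment comparisons with placebo will be based on review of descriptive statistics and individual participant data". Neither document gives a denominator in dosing periods, an exposure adjustment, or a warning that the pooled column covers twice as many periods per person as placebo.

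The Part A displays that count participants include the adverse event tables (3.1 all events, 3.5 by maximum grade, 3.8 drug-related, 3.11 common non-serious) and Table 3.44 (hepatobiliary laboratory abnormalities). Tables 3.53 and 3.56 classify participants by maximum QTc and by maximum QTc increase.

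**The concern.** Among completers the pooled active column and the placebo column contain the same people and show the same N, so they look directly comparable. They are not comparable for any row of the form 'participants with at least one event': active takes the union of two periods and placebo takes one. The active percentage will tend to be higher even if the drug does nothing.

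Safety and tolerability is a primary objective, and it is compared with placebo only by reading descriptive columns and individual data. Each dose is given to about six participants, so a pooled column is a natural place to look for a signal. Table 3.11 is also marked as a disclosure display, so a misleading excess could be carried into public results.

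**Working it through.** **Inputs from the documents**
- Two active periods and one placebo period per participant (Protocol 4.1, SAP 2.3).
- Placebo falls equally often in periods 1, 2 and 3 (Protocol 6.3.1), so a period trend does not explain or offset the effect.
- Planned Part A size: 3 cohorts × 9 = 27 (Protocol 9.2). The plan's total reproduces: 27 + 3 × 12 + 12 = 75. No power calculation, event rate or margin is given.
- SAP 5.1 lists six Part A doses. At three doses per cohort that is two cohorts, 2 × 9 = 18 participants: 18 × 2 = 36 active periods and 18 placebo periods. With three cohorts it is 54 and 27.

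**Assumptions, not in the documents**
- p: probability of at least one event in a period, the same on active and placebo (no drug effect).
- rho: correlation of the event indicator between two periods in the same participant.
- All participants complete all three periods.

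**Formula**
- P(event in both active periods) = p² + rho·p(1 - p).
- P(event in at least one active period) = 2p - p² - rho·p(1 - p).
- Dividing by p, the ratio to placebo is 2 - p - rho(1 - p). It equals 1 only when rho = 1. For rho of zero or more, 2 - p is the ceiling.

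**Results**

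| p (placebo rate) | Pooled active rate, rho = 0 | Ratio, rho = 0 | Ratio, rho = 0.2 | Ratio, rho = 0.5 |
|---|---|---|---|---|
| 0.05 | 9.8% | 1.95 | 1.76 | 1.48 |
| 0.10 | 19% | 1.90 | 1.72 | 1.45 |
| 0.20 | 36% | 1.80 | 1.64 | 1.40 |
| 0.30 | 51% | 1.70 | 1.56 | 1.35 |

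For p = 0.10 the three ratios are 2 - 0.10 = 1.90; 1.90 - 0.2 × 0.90 = 1.72; and 1.90 - 0.5 × 0.90 = 1.45. With 18 participants and rho = 0, the expected numbers with an event are 0.19 × 18 = 3.4 on active and 0.10 × 18 = 1.8 on placebo.

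**Simulation with no drug effect** (100,000 trials, independent periods, p = 0.10). With 18 participants the pooled active rate is higher than placebo in 71% of trials and lower in 15%. With 27 participants the figures are 78% and 13%.

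**After the change.** With periods as the denominator, the expected rate is p in both columns. In the simulation with 18 participants both come to 10.0%, with active higher in 46% of trials and lower in 41%. The expected rates no longer differ.

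**The case against.** The other side has several good points.

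- **The comparison the SAP lists is sound.** SAP 5.1 names each dose against placebo, which is one period against one period. The by-dose columns stay in the displays, and individual data are reviewed too. This limits the harm, but the pooled column is still required and still misleads in count rows.
- **The placebo wording sits elsewhere.** A reader might infer that the notes on the affected tables present the pooled column as a placebo comparison. They do not. The note "By dose and 'All Treatment' (treatment vs placebo) for all parameters mentioned in the protocol" is on the haematology change and percent-change tables (3.29, 3.32), which summarise change by visit and are not distorted. For the adverse event, hepatobiliary and QTc tables, the pooled column rests on the general line in SAP 13.6.1 alone.
- **The standard shells for these tables are not reproduced.** The subject unit is read from SAP 13.6.1 and from participant counts in some adverse event table titles. For Tables 3.53 and 3.56 the problem arises only if the shell takes one maximum across both active periods, which is likely but not stated.
- **'Nearly twice' is the upper end.** It needs uncommon events with little clustering within a person. Common or recurrent events give clearly smaller ratios.
- **A QTc shift in milliseconds cannot be supported.** One might infer an inflated mean maximum, but the tables are by category and the documents give no within-subject SD.
- **Part B is different.** It is parallel-group, so this mechanism does not arise. Keeping the placebo participants of the 7-day cohort apart gives that cohort a duration-matched control. Asking for one pooled placebo column there would be a preference.
- **No escalation decision is shown to depend on these rows.** In-stream review displays are outside the SAP, and the affected tables are scheduled only for the final analysis.

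Subject-level incidence among everyone exposed is also a legitimate summary. What it lacks is a comparable placebo figure beside it.

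**Conclusion.** The point holds for Part A rows that count participants with at least one event (Tables 3.1, 3.5, 3.8, 3.11 and 3.44), and conditionally for Tables 3.53 and 3.56. As specified, these rows overstate the pooled active rate relative to placebo when the drug has no effect, unless events recur perfectly within a person. For p between 0.05 and 0.30 and rho between 0 and 0.5, the ratio runs from 1.95 down to 1.35. The direction follows from the design and the SAP text. The size rests on assumed p and rho. This is a reporting defect on a primary safety objective and an inexpensive one to correct. It does not threaten the by-dose comparisons, the by-visit summaries or Part B.

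**What to change.** In SAP 13.6.1, add for Part A count and worst-case tables that the pooled active column is reported per dosing period: active periods with at least one event over all active periods (about 36 for two cohorts, 54 for three), beside placebo periods with at least one event over all placebo periods (about 18, or 27). The subject count may stay as an additional figure. If it does, extend the required footnote to say that each subject contributes two active periods and one placebo period, and that comparisons with placebo use the per-period or by-dose columns. State also whether Tables 3.53 and 3.56 take the maximum within each period or across both active periods.

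The cost is a sentence or two in the SAP, slightly more programming and a departure from the standard shell. No new data are needed.
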